There are 2 non-blinded, single-dose, single-center studies that examine the pharmacokinetics of intranasal sumatriptan in children aged 6 to 11 years (Study SUM40254) and in adolescents aged 12 to 17 years (Study SUMB1006). Both studies were conducted in patients diagnosed with migraine and demonstrated that pharmacokinetic parameters outside of a migraine attack in adolescents are similar to those previously reported in adults, suggesting that adolescents should be dosed similarly to adults. Given the dose adjustment scheme used in these studies based on age and bodyweight, there were no clinically significant differences in sumatriptan exposure between adults, adolescents, and children. Various doses and formulations of sumatriptan have been widely studied in adolescents, including subcutaneous, oral, and nasal spray formulations. Of the studies designed as placebo-controlled trials evaluating pain relief following treatment of a moderate-to-severe migraine attack, all failed to demonstrate efficacy for the primary endpoints, primarily due to high placebo response. For this reason, sumatriptan has not yet been approved by the FDA for use in adolescents with migraine. However, efficacy was demonstrated through secondary endpoints and pooled analysis suggesting a high probability of achieving pain freedom at 2 hours following treatment with 20 mg sumatriptan nasal spray. Based on these results, the 2004 American Academy of Neurology (AAN) Practice parameter on the pharmacologic treatment of migraine headache in children and adolescents concluded that sumatriptan nasal spray is effective and should be considered for the acute treatment of migraine in adolescents.

ONZETRA® Xsail® (AVP-825) is a novel intranasal delivery system containing low-dose sumatriptan powder, approved for the acute treatment of migraine with and without aura in adults (ONZETRA Xsail Prescribing Information, 2016). AVP-825 uses a Breath Powered® intranasal delivery system that widens nasal passages and naturally seals the soft palate, while using the patients' exhaled air to propel sumatriptan-powder into the nostril and deliver drug

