**6****STUDY ASSESSMENTS AND PROCEDURES****6.1 Efficacy Measures****6.1.1 Primary Measure**

Subjects will record in the diary if they are headache pain free for each migraine attack (1 and 2), at the following timepoints post dose: 15, 30, 60, 120 mins, 3, 4, and 24 hours.

The primary endpoint is headache pain-free at 120 minutes following treatment of Migraine Attack 2.

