### 8.2 Efficacy Analysis

The primary efficacy endpoint of the study is headache pain-free at 120 minutes following treatment of Migraine Attack 2. Treatment comparison will be performed by using the Cochran-Mantel-Haenszel (CMH) test stratified by age group (12-14 years or 15-17 years) and baseline migraine pain severity (moderate or severe). Secondary and exploratory efficacy endpoints will be analyzed similarly, or appropriate statistical tests will be used. Efficacy assessments after taking rescue medication will be set to missing. Missing data will be imputed by treatment failure, i.e., headache pain-free = no. *Secondary efficacy endpoints (Migraine Attack 2):*

- Headache relief (defined as a reduction in pain intensity from moderate or severe [grade 2 or 3] at baseline to none or mild [grade 0 or 1] at 120 minutes)
- Headache pain-free by time (other than at 120 minutes)
- Headache relief by time (other than at 120 minutes)
- Change from baseline in headache severity by time
- Sustained pain relief, defined as headache relief [headache severity mild (grade 1) or none (grade 0)] at 2 hours with no worsening of headache, use of a second dose of study medication, or rescue medication taken through 24 hours after dose
- Sustained pain freedom, defined as pain freedom [headache severity none (grade 0)] at 2 hours with no recurrence of headache, use of a second dose of study medication or rescue medication taken through 24 hours after dose
- Rescue medication use and time to rescue medication
- Number of subjects with nausea, phonophobia, photophobia, or vomiting by time
- Number of subjects who return to ‘normal’ functioning by time

---

- Time to recurrence of headache defined as an increase from a headache severity score of 0 (none) or 1 (mild) at 2 hours to 2 (moderate) or 3 (severe) within 24 hours

*Exploratory efficacy endpoints (Migraine Attack 2):*

- Sustained pain relief (1 to 2 hours), defined as headache relief [Headache severity mild (grade 1) or none (grade 0)] at 60 minutes with no worsening of headache, use of a second dose of study medication, or rescue medication taken through 120 minutes after dose
- Sustained pain freedom (1 to 2 hours), defined as pain freedom [Headache severity none (grade 0)] at 60 minutes with no recurrence of headache, use of a second dose of study medication or rescue medication taken through 120 minutes after dose
- Bilateral headache at predefined timepoints

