## **8.4 Sample Size Calculations**

Power calculations are based on the results of the completed pivotal trial for adults (OPN-SUM-MIG-3301, Avanir data on file). The observed percentage (n) of subjects experiencing migraine headache pain free at 120 minutes was 34.3% (37) vs. 17.3% (18) for AVP-825 vs. placebo, respectively. For this study in adolescents with single-blind placebo run-in, if it is assumed that the percentage of subjects who are migraine headache pain free at 120 minutes is 30% vs. 15%, a sample size of 236 (118/arm) randomized and treated at Migraine Attack 2 would provide approximately 80% power with 2-sided  $\alpha = 0.05$ . In consideration of the attrition rate during the run-in phase, it is estimated that 420 subjects would be needed to enter the single-blind placebo run-in phase in order to have approximately 236 subjects randomized and treated for Migraine Attack 2.

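### Section 8.2 sets no gate, order or nominal label for roughly 25 to 50 secondary comparisons, so a secondary efficacy claim would carry no error control

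*Combined protocol and SAP*

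**What the plan says.** Section 8.2 names a single primary: "The primary efficacy endpoint of the study is headache pain-free at 120 minutes following treatment of Migraine Attack 2". It is tested by a Cochran-Mantel-Haenszel test stratified by age group and baseline pain severity. The rule for the remaining endpoints is one sentence: "Secondary and exploratory efficacy endpoints will be analyzed similarly, or appropriate statistical tests will be used". The synopsis has nearly the same sentence for the secondaries.

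Ten secondary endpoints are then listed. Five are by time: pain-free, relief, change in severity, the four associated symptoms, and return to normal functioning. Four exploratory endpoints follow.

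Neither section 8.2 nor the synopsis gives a significance level for secondaries, a key secondary endpoint, a testing order, a condition that the primary succeeds, a multiplicity adjustment, or a statement that secondary p-values are descriptive. The 0.05 level appears only with the sample size (section 8.4 and the synopsis). The matter is not deferred to another analysis document. No interim analysis is planned (8.3.1).

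Section 1 reports that earlier placebo-controlled adolescent sumatriptan trials of pain relief missed their primary endpoints, largely because of high placebo response. It then says that "efficacy was demonstrated through secondary endpoints and pooled analysis".

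**The concern.** A sound primary test does not protect conclusions drawn from other comparisons. With many secondary comparisons and no rule for reading them, one that crosses 0.05 by chance can be put forward as evidence of efficacy, including after a failed primary.

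That situation is realistic here. Section 1 gives high placebo response as the reason why earlier adolescent trials missed, and the planned power leaves about one chance in five of missing even if the assumed effect is real. Section 1 also shows that secondary and pooled results have been cited as demonstrating efficacy for this drug class and age group. The plan does not say how such results would be read in this trial.

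**Working it through.** **The plan's own figure.** Inputs from section 8.4: "a sample size of 236 (118/arm) randomized and treated at Migraine Attack 2", 30% vs 15%, two-sided 0.05, about 80% power.

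- Unpooled variance: n per arm = (1.960 + 0.842)² × (0.30×0.70 + 0.15×0.85) / 0.15² = 7.849 × 0.3375 / 0.0225 = 117.7, so 118. Power at 118 per arm is 80.1%.
- Pooled variance: 121 per arm. Power at 118 per arm is 79.2%.

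The figure reproduces. The chance of missing the primary under the assumed effect is therefore about 20% (19.9% to 20.8%).

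**Number of comparisons.** The plan states none, so it has to be counted. Section 6.1.1 gives the pain-free times as "15, 30, 60, 120 mins, 3, 4, and 24 hours", seven in all. Table 2 gives five post-dose times for symptoms and functioning. The synopsis text lists only five times for all measures. The severity row of Table 2, as it reads in the extracted text, marks only pre-dose and 15 minutes. That may be a broken row, so both readings are counted.

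| Endpoint | Full reading | Synopsis times | Narrowest reading |
|---|---|---|---|
| Relief at 120 min | 1 | 1 | 1 |
| Pain-free, other times | 6 | 4 | 6 |
| Relief, other times | 6 | 4 | 1 |
| Change in severity | 7 | 5 | 2 |
| Sustained relief, sustained freedom | 2 | 2 | 2 |
| Rescue use, time to rescue | 2 | 2 | 2 |
| Symptoms | 4 × 5 = 20 | 20 | 5 (one composite) |
| Normal functioning | 5 | 5 | 5 |
| Time to recurrence | 1 | 1 | 1 |
| Total | 50 | 44 | 25 |

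The narrowest reading takes severity at 15 minutes and at 120 minutes, where the relief endpoint needs it. Exploratory endpoints are left out of all three counts.

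**Chance of a spurious result favouring active, no effect on anything.** Each test has a 2.5% chance of significance in that direction. The expected number is 25 × 0.025 = 0.6 to 50 × 0.025 = 1.25, whatever the correlation. For independent tests the chance of at least one is 1 − 0.975^m, which is 46.9% for m = 25 and 71.8% for m = 50. For correlated tests, normal test statistics with equal correlation ρ were simulated (200,000 draws). The documents give no correlation, so ρ is an assumption.

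| ρ | 25 comparisons | 44 | 50 |
|---|---|---|---|
| 0 | 47% | 67% | 72% |
| 0.3 | 32% | 42% | 45% |
| 0.5 | 24% | 30% | 32% |
| 0.7 | 16% | 19% | 20% |
| 0.9 | 8% | 10% | 10% |

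Among trials in which the primary does not favour active significantly, the range for ρ = 0.7 to 0.3 is 14% (25 comparisons) to 44% (50 comparisons).

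As a sensitivity check, correlation was allowed to depend on endpoint domain and time apart (50 comparisons, average correlation 0.14 to 0.51). This gave 27% to 52% overall, and 25% to 51% when the primary missed.

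**With a gate and fixed sequence.** Any secondary claim requires the primary to be significant first. If each step must favour active at two-sided 0.05, then P(any secondary claim favouring active) ≤ P(primary significant favouring active) = 2.5% under no effect, for any correlation. The sample size stays at 236.

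**The case against.** The strongest reply is that the plan never says each timepoint gets its own formal test, or that any secondary result will support a claim. The governing sentence allows other appropriate methods, and some endpoints are worded as counts. A longitudinal analysis or a simple tabulation would fit the text. This stands as a reason to give a range for the count. It does not supply the missing rule.

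A reader might infer that a chance secondary finding is likely, from 1 − 0.95^50 = 92%. The documents do not support that. The figure needs 50 independent tests and includes results favouring placebo. Pain-free, relief, severity and sustained response all come from ratings of the same headache in one attack, so independence is implausible. Counting only results favouring active, under the equal-correlation model, the chance exceeds one half only when the tests are near independent and the count is at the high end.

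A reader might also take section 1 as a statement of intent to claim efficacy from secondaries. It describes other trials, refers to pooled analysis as well as secondary endpoints, and says that sumatriptan remained unapproved by the FDA in adolescents because the primaries failed. It shows that such results get cited, not that this trial will rely on them.

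Finally, gating has a real cost, and the choice of sequence is partly preference. Section 1 notes that an earlier adolescent triptan indication covered pain but not associated symptoms, so the sponsor may want a symptom endpoint in the sequence. That is a fair point, and it is why the order is left to the sponsor.

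**Conclusion.** The gap is real and moderate. Section 8.2 leaves roughly 25 to 50 secondary comparisons with no gate, order or nominal label. Under no effect, the chance of at least one nominally significant result favouring active is about 16% to 45% for assumed equal correlations of 0.7 to 0.3, against at most 2.5% for a false claim under a gated fixed sequence. These figures rest on the counted range, the assumed correlations and one formal test per endpoint and time.

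It would be wrong to conclude that the primary's error rate is inflated. There is one primary endpoint, one active arm and no interim look, so the primary conclusion is untouched. The weakness concerns only what may be said from the secondaries.

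**What to change.** Add to section 8.2, and mirror in the synopsis:

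- Confirmatory secondary claims are made only if the primary has two-sided p < 0.05 in favour of active.
- They are then tested at two-sided 0.05 in a short fixed sequence, stopping at the first endpoint that is not significant in favour of active. The sponsor chooses the sequence before unblinding. One example is headache relief at 120 minutes, then sustained pain freedom to 24 hours, then sustained relief to 24 hours. All three are yes/no endpoints, so the primary's stratified test can be named for each.
- All other endpoints and timepoints, and all exploratory endpoints, are reported with nominal p-values that support no efficacy claim.

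If no secondary claim is wanted, one sentence making all secondaries descriptive would be enough.

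The change needs wording only: no added subjects, visits or data. The cost is that no secondary claim is possible when the primary misses, about 20% of the time even if 30% vs 15% is true. Endpoints after the first failed step, or outside the sequence, cannot support a claim.

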**Table 2 Time and Event Schedule for Migraine Attacks 1 and 2**

	Pre-Dose	Dosing	15 min	30 min	60 min	120 min	3 Hours	4 Hours	24 Hours
Record efficacy assessments in diary:									
Pain free (Yes/No)			X	X	X	X	X	X	X
Headache severity score	X		X 						
Migraine symptoms (separate questions): Nausea, vomiting, photophobia, phonophobia	X		X	X	X	X			X
Dose of study drug medication		X							
Bilateral headache (Yes/No)	X		X 		X 				
Intensity increased by movement (Yes/No)	X		X 		X 				
Ability to function question	X		X	X	X	X			X
Time of recurrence of headache						X 			X 
Rescue medication						X 			X 

Min = minutes;

1 Assessed only if response to pain free question is "No"

2 Assessment should be made after 120 minutes.

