### 3 STUDY DESIGN

This is a Phase 3, multicenter, randomized, double-blind, placebo-controlled study evaluating AVP-825 for the acute treatment of migraine with or without aura in adolescent subjects (12 to 17 years old). This study includes 2 treatment phases; a single-blind placebo run-in phase and a double-blind placebo-controlled treatment phase. A schematic of the study design is presented in [Figure 1](#).

Approximately 420 subjects will be enrolled in the single-blind placebo run in phase to obtain approximately 236 subjects randomized in the double-blind treatment phase. Subjects will be enrolled in the study for up to approximately 28 weeks; with up to 12-weeks in a single-blind placebo run-in period, and up to 12-weeks in a double-blind treatment period. An exit/early termination visit will occur 10 days after treatment of Migraine Attack 2. The investigational product in this study is ONZETRA Xsail 22 mg (AVP-825, sumatriptan nasal powder 11 mg per nosepiece) and the control treatment is the same device as AVP-825 with matching placebo nosepieces filled with lactose (i.e. contain no active drug).

All eligible subjects will treat one migraine attack of moderate to severe intensity during the single-blind phase (Migraine Attack 1). Placebo non-responders (defined as subjects who are not headache pain free 2 hours after treatment of Migraine Attack 1) who meet all inclusion/exclusion criteria will be randomized in a 1:1 ratio (active: placebo) to treat one migraine attack of moderate to severe intensity in the double-blind treatment phase (Migraine Attack 2). Randomization will be stratified by age (12 to 14 years versus 15 to 17 years). Enrollment will be monitored to ensure that number of subjects in either age group does not exceed 70% or drop below 30%. Study medication will be administered as soon as possible after the development of a migraine attack associated with moderate-to-severe headache pain during each phase, per the instructions for use (IFU) provided to the subject, and relevant data will be collected in a subject diary.

There are up to 3 scheduled clinic visits including: screening/enrollment (Visit 1), randomization (Visit 2), and exit/early termination (Visit 3). Monthly follow-up phone calls will be made after Visits 1 and 2 for up to 12 weeks after the visit, depending on when Migraine Attacks 1 and 2 are treated.

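### Section 8.2 does not pre-specify adjustment of the symptom and function endpoints for the same item recorded before dosing, which gives up some power for the commoner symptoms

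*Combined protocol and SAP*

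**What the plan says.** Section 8.2 names one test, for the primary endpoint: a CMH stratified by age group (12-14 or 15-17 years) and baseline migraine pain severity (moderate or severe). For the rest it says: "Secondary and exploratory efficacy endpoints will be analyzed similarly, or appropriate statistical tests will be used". The synopsis is no more specific.

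Two groups of secondary endpoints matter here. One is "Number of subjects with nausea, phonophobia, photophobia, or vomiting by time". The other is the number of subjects back to normal functioning by time. Neither is given a stratum or covariate for the value of the same item before dosing. The only endpoint defined as a change from baseline is headache severity.

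The pre-dose values exist. Table 2 marks the pre-dose column for "Migraine symptoms (separate questions): Nausea, vomiting, photophobia, phonophobia" and for "Ability to function question". Section 6.1.2 gives yes/no answers for each symptom and a five-point scale for function.

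**The concern.** Whether a subject has nausea two hours after dosing plausibly depends on whether nausea was present at dosing. If so, a comparison that mixes subjects with and without the symptom at dosing carries avoidable variance. The planned pain-severity stratum suits the pain endpoints, but for a symptom it is only an indirect stand-in for that symptom's own baseline.

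At stake is power on secondary endpoints, with data the diary already collects. Section 1 records that an earlier adolescent triptan indication covered pain but not the associated symptoms, so the symptom results have some interest. There is also a pre-specification point: if adjustment is chosen after the symptom data are seen, it loses much of its credibility.

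**Working it through.** **1. The plan's own figure.** Section 8.4 says that "a sample size of 236 (118/arm) randomized and treated at Migraine Attack 2" "would provide approximately 80% power with 2-sided" alpha 0.05, for pain-free rates of 30% and 15%. The unpooled formula gives

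n per arm = (1.960 + 0.842)² × (0.30×0.70 + 0.15×0.85) / 0.15² = 117.7, so 118.

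Power at 118 per arm with the pooled null variance is 79.2%. The figure reproduces, but it concerns the primary endpoint only. No power is stated for symptoms or function.

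**2. The test.** With stratum k holding N_k subjects, n1_k on active, n0_k on placebo, m_k with the symptom and a_k of those on active,

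Q = [Σ(a_k − n1_k·m_k/N_k)]² / Σ[n1_k·n0_k·m_k·(N_k − m_k) / (N_k²(N_k − 1))],

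rejecting when Q > 3.841. The planned version has 4 strata (age × pain severity). Adding the pre-dose item makes 8.

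**3. A hand check.** Assumed rates: symptom present before dosing in 50%; if present, still present in 60% (placebo) and 42% (active); if absent, new in 10% and 7%.

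- Average difference: 0.5×0.18 + 0.5×0.03 = 0.105.
- Ignoring the pre-dose item, the arm rates are 35% and 24.5%. Variances: 0.35×0.65 = 0.2275 and 0.245×0.755 = 0.1850. SE = √(0.4125/118) = 0.0591; z = 1.78; power = Φ(1.78 − 1.96), about 43%.
- Within pre-dose groups, variances are 0.5×0.24 + 0.5×0.09 = 0.165 and 0.5×0.2436 + 0.5×0.0651 = 0.1544. SE = √(0.3194/118) = 0.0520; z = 2.02; power = Φ(2.02 − 1.96), about 52%.

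**4. Simulation of the actual CMH, same assumed rates, 118 per arm.**

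| Pre-dose prevalence | Planned CMH | With pre-dose item |
|---|---|---|
| 5% | 15% | 15% |
| 10% | 18% | 19% |
| 35% | 32% | 38% |
| 50% | 42% | 50% |
| 65% | 53% | 60% |
| 85% | 68% | 72% |
| 90% | 72% | 75% |

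Repeat runs moved these by 1 to 2 points; one gave 42% to 51% at 50% prevalence. With a weaker association at 50% prevalence (placebo 50%/25%, active 33%/14%), power goes from 65% to 67%.

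**5. A second set of assumptions** (common odds ratio 0.45, 8,000 trials per scenario):

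- 50% prevalence, placebo 60% if present and 10% if absent: 56% to 66%.
- 50% prevalence, very strong persistence (70%/5%): 42% to 60%.
- 50% prevalence, weak association (50%/25%): 74% to 75%.
- 50% prevalence, no association: 80.5% to 79.6%.
- Prevalence 80-90%: 73-81% to 79-83%.
- Prevalence 5% and 10%: 15% to 15%, and 24% to 25%.

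Letting the pre-dose symptom depend on pain severity (35% if moderate, 65% if severe) leaves the gain almost unchanged, at 56% to 66%. The planned pain stratum does not recover it.

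**6. Function** (odds ratio 2.2; four assumed pre-dose grades holding 20%, 40%, 25% and 15% of subjects):

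| Dependence on pre-dose grade | Planned | Two levels (8 strata) | Four grades (16 strata) |
|---|---|---|---|
| Strong | 66.3% | 70.3% | 71.6% |
| Moderate | 73.3% | 74.2% | 73.0% |
| None | 80.4% | 79.7% | 77.9% |

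**7. Type I error.** With no treatment effect, the second-set and function simulations rejected in 4.4% to 5.3% of trials, with or without the extra stratum.

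**The case against.** The strongest objection is that the plan does not commit to leaving the pre-dose value out. Its wording allows other appropriate tests, and a baseline-adjusted test would qualify. That stands. A reader might infer that Section 8.2 fixes an unadjusted comparison; the text supports only that adjustment is not pre-specified and that the one named analysis omits it. Nor is the named analysis wholly unadjusted, since it stratifies by age and pain severity.

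A reader might infer that all five items lose power. They do not: the gain vanishes for a rare symptom and is small or nil for function unless the pre-dose grade predicts return to normal strongly.

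A reader might also infer that chance imbalance in the pre-dose item biases the result. Randomisation already allows for it. With 50% prevalence and no effect, about 14% of simulated trials had an imbalance of at least 10 points; in those the planned CMH rejected 13.6% of the time, against 4.3% with the extra stratum. That is a conditional property of an unlucky trial. Over all trials the error rate stays near 5%.

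Finally, the consequence is limited. The trial was sized for the primary endpoint, Section 2 states no symptom objective, and in the step 4 scenarios at 35% to 65% prevalence power remains only 38% to 60% after the change.

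**Conclusion.** The point holds as an efficiency and pre-specification gap on secondary endpoints. The gain is about 2 to 9 points for symptoms present before dosing in roughly 35% to 85% of subjects. It reaches 10 points under the 60%/10% contrast with odds ratio 0.45, and 18 under very strong persistence. It is about zero for a vomiting-like item and about -2 to +5 points for function. If the item is not prognostic, about 1 point is lost, or about 2 with 16 sparse function strata.

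Every rate behind these figures is an assumption, including the strength of the pre-dose association; the documents supply only the sample size, the test and the schedule. The direction is well supported, the size is not. There is no bias, no inflation of type I error and no effect on the primary analysis.

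**What to change.** In Section 8.2, and in matching words in the synopsis, state:

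- Nausea, photophobia and phonophobia are each tested by CMH stratified by age group, baseline pain severity and pre-dose presence of that symptom. Treat vomiting the same way for consistency, without expecting a gain: at 5% prevalence only about 0.05×236 = 12 subjects would have it before dosing, about 3 per age-by-severity cell.
- Return to normal functioning is tested in all mITT subjects by CMH stratified by age group, baseline pain severity and pre-dose function rating in two levels, with the cut written into the text. Two levels lose under 1 point if the rating is not prognostic, against about 2 with four grades.
- Say how subjects already rated normal before dosing are counted, which the plan leaves unsaid. A summary restricted to subjects not normal before dosing is supportive only, because Section 8.1 assigns all efficacy analyses to the mITT population.

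Keep pain severity as a stratum; dropping it buys at most about 2 points. The cost is a few sentences before unblinding. No new data are needed and the sample size does not change.
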